Appendix 2 Details of Futility Analysis

An unmasked interim analysis will be conducted for futility assessment by the IDMC when approximately 50% of the total planned AC-determined NMO/NMOSD attacks occur in this study. This will be triggered when approximately 34 AC-determined NMO/NMOSD attacks occur in the ITT population. The assessment of futility will be based on predictive power, which is based on the average conditional power calculated at the observed treatment effect at the time of the interim analysis. The study will be considered futile if the predictive power is < 20% in both the ITT population AND the AQP4-IgG seropositive cohort. Figure 7-6 provides estimated predictive power when observed treatment effect varies from 0 to 90% in relative reduction in risk of an AC-determined NMO/NMOSD attack in the ITT population. The 20% predictive power translates into a treatment effect of approximately 27%. A value of 50% and 90% predictive power will result in 43% and 60% treatment effects, respectively, which are minimally detectable treatment effect and target treatment effect for this study. The actual predictive power will be calculated based on observed data.

[figure not shown]

Figure 7-6 Estimated Predictive Power Against Observed Interim Treatment Effect When 50% of AC-determined NMO/NMOSD Attacks are Available

AC = Adjudication Committee; HR = hazard rate; NMO/NMOSD = neuromyelitis optica/neuromyelitis optica spectrum disorders

Appendix 3 Type I Error Control

To establish Type I error control, the primary endpoint, and the 4 secondary endpoints will be denoted by E1 through E5, respectively, as follows:

- E1: Time to AC-determined NMO/NMOSD attack
- E2: Worsening from baseline in EDSS at last visit during the RCP
- E3: Change from baseline in low-contrast visual acuity binocular score measured by low-contrast Landolt C Broken Rings Chart, at last visit during RCP
- E4: Cumulative total active MRI lesions (new Gd-enhancing or new/enlarging T2) during the RCP
- E5: Number of NMO/NMOSD-related in-patient hospitalizations

Based on 2 populations of interest (seropositive and ITT populations), this will result in testing 10 null hypotheses of no treatment effect labeled as follows (Table 7-5):

Table 7-5 List of Null Hypotheses Considered Under Multiplicity Adjustment Procedure

Hypothesis	Test
S1	Test E1 in seropositive subjects
S2	Test E2 in seropositive subjects
S3	Test E3 in seropositive subjects
S4	Test E4 in seropositive subjects
S5	Test E5 in seropositive subjects
O1	Test E1 in ITT population
O2	Test E2 in ITT population
O3	Test E3 in ITT population
O4	Test E4 in ITT population
O5	Test E5 in ITT population

The multiplicity adjustment strategy based on Bonferroni-based chain procedure ([Bretz et al, 2009](#); [Millen and Dmitrienko, 2011](#)) for testing these 10 hypotheses is defined in Figure 7-7. Each hypothesis is represented by a rectangular box. The connections among the hypotheses are visualized using arrows. A solid arrow is used to define the decision path after a hypothesis is rejected, eg, the hypothesis O1 is tested if and only if the hypothesis S1 is rejected. The Bonferroni-based chain procedures are characterized by 2 rules:

- The alpha allocation rule specifies the initial distribution of the Type I error rate among the null hypotheses according to the relative importance of the null hypotheses

- The alpha propagation rule determines the process of re-distributing the available Type I error rate among the non-rejected null hypotheses after each rejection

[figure not shown]

Figure 7-7 Multiplicity Adjustment Strategy

The alpha allocation rule is specified in Table 7-6. Specifically, the null hypothesis S1 receives the initial weight of 1 (ie, it is tested at the full $\alpha = 0.05$) and the other null hypotheses receive zero weights. The alpha propagation rule is specified in Table 7-7. The alpha propagation rules are defined using transition parameters, eg, the first row in Table 7-7 shows that the fraction of the Type I error rate used in testing the null hypothesis S1 will be transferred to the null hypothesis O1 if the null hypothesis S1 is rejected. Similarly, if the null hypothesis O1 is rejected, the available Type I error rate will be split equally among the null hypotheses S2, S3, S4, and S5 (a quarter of the available Type I error rate will be allocated to each null hypothesis). The alpha allocation and alpha propagation rule uniquely define the Bonferroni-based chain procedure and the associated multiplicity-adjusted p-values can be computed using Algorithm 2 given in [Bretz et al \(2009\)](#).

Table 7-6 Alpha Allocation Rule	
Hypothesis	Initial Alpha Allocation
S1	α
S2	0
S3	0
S4	0
S5	0
O1	0
O2	0
O3	0
O4	0
O5	0

Table 7-7 Alpha Propagation Rule										
Hypothesis	S1	S2	S3	S4	S5	O1	O2	O3	O4	O5
S1	0	0	0	0	0	1	0	0	0	0
S2	0	0	0	0	0	0	1	0	0	0
S3	0	0	0	0	0	0	0	1	0	0
S4	0	0	0	0	0	0	0	0	1	0
S5	0	0	0	0	0	0	0	0	0	1
O1	0	1/4	1/4	1/4	1/4	0	0	0	0	0
O2	0	0	1/3	1/3	1/3	0	0	0	0	0
O3	0	1/3	0	1/3	1/3	0	0	0	0	0
O4	0	1/3	1/3	0	1/3	0	0	0	0	0
O5	0	1/3	1/3	1/3	0	0	0	0	0	0

Appendix 4 Neuromyelitis Optica Attack Severity Score

Study CD-IA-MEDI-551-1155 is aimed at assessing the efficacy and safety of MEDI-551 in subjects with history of NMO/NMOSD who experienced at least one episode of attack. The primary endpoint is the time to an attack based on predefined criteria. The diagnosis of an attack, determined by the principal investigator at the investigational site will be reviewed and adjudicated by an AC. None of the endpoints in the study are based on the assessment of the severity of an attack. In discussion with experts in the field and with the FDA the significance of assessing the severity of NMO attack as exploratory analysis became apparent. There are no well-established and tested criteria to assess the severity of NMO/NMOSD attack. The criteria presented here are based on some data available in the literature ([Pittock et al](#)) and on an input from experts in the field. This scoring system is

exploratory in nature and its relevance and applicability will be assessed at the end of this study.

NMO/NMOSD attack severity score

A severity classification for each type of NMO/NMOSD attack (Optic Neuritis, Myelitis, Brain and Brainstem) is described in subsequent sections based on the respective subscale. Severity assessment (graded as ‘minor’ or ‘major’) will be based on a ‘shift’ in subscale scores corresponding to the domain of interest at the time of attack from the last assessment of the subscale.

When measured at the follow-up visit post an NMO/NMOSD attack, the ‘shift’ in the subscale score at the follow visit from the time of attack will be used to grade the ‘recovery or improvement’ as well (graded as ‘minor’ or ‘major’).

Subscale for each domain

Table 7-8 provides the subscales corresponding to each domain mentioned above. The V_A represents the corrected visual acuity assessment based on high-contrast Landolt Broken Ring C-chart.

Table 7-8 Subscale Score by Domain of NMO/NMOSD Attack

Domain	Subscale Score	Description
ON	0	Normal
	1	Scotoma ^a but $V_A \geq 50$ characters
	2	$V_A \geq 35-49$ characters
	3	$V_A \geq 20-34$ characters
	4	$V_A \geq 1-19$ characters
	5	Counting fingers only
	6	Light perception only
Myelitis	7	No light perception
	0	Normal
	1	Abnormal signs (hyperreflexia, Babinski sign) without weakness
	2	Mild weakness (MRC grade 5- or 4+) in affected limb(s)
	3	Moderate weakness (grade 3 or 4) in 1 or 2 UMN muscles in affected limb(s)
	4	Moderate weakness (grade 3 or 4) in 3 UMN muscles in affected limb(s)
	5	Severe weakness (grade 2) in 1 or more muscles in affected limb(s)
6	Some plegic (grade 0 or 1) muscles in 1 or more limbs	
7	Plegia (grade 0 or 1) of all muscles in 1 or more limbs	
Brain	0	Normal

Table 7-8 Subscale Score by Domain of NMO/NMOSD Attack

Domain	Subscale Score	Description
	1	Drowsiness or mood changes only
	2	Mild confusion/disorientation (able to manage all self-care functions); mild focal impairment (mild aphasia, apraxia, agnosia, anorexia or drowsiness)
	3	Moderate confusion/disorientation (able to manage some self-care functions); moderate focal impairment (moderate aphasia, apraxia, agnosia, anorexia or drowsiness)
	4	Severe confusion/disorientation (unable to manage self-care functions); severe focal impairment (aphasia such that is unable to comprehend simple one step commands or speak 5 word sentences; severe apraxia, agnosia, anorexia or drowsiness)
	5	Stupor or coma
Brainstem	0	Normal
	1	Signs only (unsustained nystagmus, impaired saccadic pursuit, ocular dysmetria, mild facial weakness or sensory loss)
	2	Sustained conjugate nystagmus, incomplete INO, moderate facial weakness or sensory loss, or other mild disability; mild nausea and vomiting for 48 hours or longer without other explanation with vomiting not more than 3 times per day; intractable hiccups occurring more than 20 times per hour less than 6 hours per day
	3	Dyconjugate nystagmus (INO) or severe extraocular weakness, loss of facial sensation or facial paralysis (unilateral or bilateral), moderate dysarthria or dysphagia; moderate nausea and vomiting lasting 48 hours or longer without other explanation with vomiting between 3 and 7 times per day; intractable hiccups occurring more than 20 times per hour for 6 to 12 hours per day
	4	Severe dysarthria or dysphagia, almost complete ophthalmoplegia, or other severe disability of a cranial nerve/nerves; severe nausea and vomiting lasting 48 hours or longer without other explanation with vomiting occurring more than 7 times per day; intractable hiccups occurring more than 20 times per hour for more than 12 hours per day
	5	Inability to swallow or speak because of bulbar dysfunction; respiratory failure requiring intubation because of brainstem lesion.

^a Scotoma assessment can be obtained from EDSS/FSS

Severity assessment

Based on the subscale score described in Table 7-8, the severity assessment of each type of NMO/NMOSD attack is provided in Table 7-9.

Table 7-9 NMO/NMOSD Attack Severity Grade

Domain	Subscale score at visit prior to attack	Subscale score at time of attack	Severity
ON, Myelitis, Brainstem	< 2	< 3	Minor
		≥ 3	Major
	≥ 2	Increase by 1 point	Minor
		Increase by ≥ 2 points	Major

Table 7-9 NMO/NMOSD Attack Severity Grade

Domain	Subscale score at visit prior to attack	Subscale score at time of attack	Severity
Brain	Not applicable	Increase by 1 point	Minor
		Increase by ≥ 2 points	Major
		Increase by 1 point	Minor
		Increase by ≥ 2 points	Major

Recovery assessment

Based on the subscale score described in Table 7-8, the recovery assessment of each type of NMO/NMOSD attack is provided in Table 7-10.

Table 7-10 NMO/NMOSD Attack Recovery Grade

Domain	Subscale score at time of attack	Improvement ^a at follow up visit	Recovery
ON, Myelitis, Brainstem	Any score	≤ 2	Minor
	≥ 3	> 2	Major
Brain	Any score	1	Minor
	≥ 2	>1	Major

^a Improvement at follow up visit = Change from attack in subscale scores at follow up visit.

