- The last line the subject is able to see and read correctly determines the score

The following visual acuity data are to be reported by the ophthalmology examiner:

- Low-contrast visual acuity score for each eye separately and both eyes together
- High-contrast visual acuity score for each eye separately and both eyes together
- If a subject cannot read any lines on the chart, visual acuity will be tested by counting fingers (CF), hand movement (HM), or light perception (LP) at 1 meter, or no light perception (NLP)/total blindness.

Assessment of Relative Afferent Pupillary Defect

For the purposes of this study, RAPD will be assessed by the "swinging light test," a method of detecting differences between the two eyes in how the pupils respond to light shone in one eye at a time. This test must be administered by an ophthalmologist or another site member with appropriate training and experience (ie, not the investigator) and in accordance with standard of care at the institution. If possible, the same ophthalmology examiner should review a single subject through every assessment.

The RAPD test can be useful in detecting unilateral or asymmetric disease of the retina or optic nerve. The physiological basis of the test is that in healthy eyes the reaction of the pupils in the left and right eyes are linked; that is, a bright light shone in one eye will lead to equal constriction of both pupils. A RAPD is present if the initial consensual pupillary constriction is greater than the initial direct pupillary constriction.

The following procedures are recommended:

- Perform the test in a semi-darkened room. If the room is too dark it will be difficult to observe pupil responses, particularly in heavy pigmented eyes
- Use a bright torch such as a small flashlight that can be focused to provide a narrow, even beam of light
- Ask the subject to focus on a distant object and keep looking at it – use a chart or picture as an object of focus
- Move the flashlight from side to side so the beam of light shines directly into each eye. Do not swing the beam from side to side around a central axis (eg, by holding it in front of the subject’s nose) as this can stimulate the near response
- Keep the light source at the same distance from each eye to ensure the light stimulus is equally bright in both

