3.5.4 Other Efficacy Analyses

Table 3.5.4-1 provides an overview of additional efficacy analyses to be performed.

Table 3.5.4-1 Additional Efficacy Analyses

Type of analysis	Analysis Method	Analysis population
Cox proportional hazards model of investigator-determined NMO/NMOSD attack	Similar analysis as primary endpoint but based on investigator-determined NMO/NMOSD attack.	ITT
Time to either AC-determined NMO/NMOSD attacks or rescue therapy	An exploratory analysis of time to adjudicated AC-determined NMO/NMOSD attacks or rescue therapy (where an attack has not been determined by AC) during the RCP will be conducted by considering administration of rescue therapy as an event of interest. Subjects who never experience an NMO/NMOSD attack (determined by AC) nor received any rescue therapy will be censored for this analysis. In the instance where a subject never experiences an AC-determined NMO/NMOSD attack, the time to rescue therapy will be used for this analysis.	ITT
Type of NMO/NMOSD attacks	Number (%) of subjects with different types of NMO/NMOSD attacks (ON, Myelitis, Brain and Brainstem) (subjects will be included in multiple categories if applicable): 
 • Based on AC-determined attacks • Based on investigator-determined attacks 	ITT
Summary of individual criteria of NMO/NMOSD attack	Number (%) of subjects meeting each of the protocol-defined criteria for NMO/NMOSD attack will be summarized descriptively (subjects will be included in multiple categories if applicable): 
 • Based on AC-determined attacks • Based on investigator-determined attacks 	ITT
Criteria based severity of attack	Number (%) of subjects meeting each of the protocol-defined criteria of an AC-determined NMO/NMOSD attack will be summarized broken down by the severity [mild, moderate, severe] defined in Table 3.4.1.4-1	ITT
Attack type based severity	Number (%) of subjects meeting an AC-determined NMO/NMOSD attack will be summarized broken down by the severity [minor, major] defined in Appendix 4	ITT

Table 3.5.4-1 Additional Efficacy Analyses

Type of analysis	Analysis Method	Analysis population
Attack recovery	Number (%) of subjects meeting an AC-determined NMO/NMOSD attack will be summarized broken down by the recovery status [minor, major] defined in Appendix 4	ITT

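### SAP Table 7-10 has no grade for an attack that does not recover, and its footnote leaves the direction of change open

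*SAP*

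**What the plan says.** SAP Appendix 4 sets up an exploratory score for each attack domain. In Table 7-8 each subscale starts at 0 (normal) and rises with severity, to 7 for ON and myelitis and to 5 for brain and brainstem. The text says that the shift "in the subscale score at the follow visit from the time of attack will be used to grade" recovery, and that recovery is "graded as ‘minor’ or ‘major". No third grade is named.

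Table 7-10 then gives the rules:

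- ON, myelitis, brainstem: Minor is "Any score ≤ 2 Minor" (the table cells read across). Major needs an improvement above 2 and an attack score of at least 3.
- Brain: Minor is "Any score 1 Minor". Major needs an improvement above 1 and an attack score of at least 2.

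Footnote a defines the graded quantity: "Improvement at follow up visit = Change from attack in subscale scores at follow up visit".

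SAP Section 3.5.4, Table 3.5.4-1, uses the result as a number (%) of ITT subjects with an adjudicated attack, "broken down by the recovery status [minor, major] defined in Appendix 4".

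On visual acuity, Protocol Section 4.3.1.3 says that when no chart line can be read, "visual acuity will be tested by counting fingers (CF), hand movement (HM), or light perception (LP) at 1 meter", followed by no light perception. The ON subscale in Table 7-8 has level 5, "Counting fingers only", and then goes straight to light perception at level 6.

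**The concern.** A recovery table should separate attacks that got better from those that did not. With two grades and no lower bound on Minor, a subject whose score has not moved is counted as having recovered. The Brain row treats the same outcome differently and leaves it blank, so the domains cannot be combined or compared.

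The direction of change is a second weakness. Because higher scores are worse, *change from attack*, computed in the usual way as follow-up minus attack, is negative when a subject improves. That conflicts with the column heading Improvement. Two programmers could each defend their choice and produce different tables.

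The cases involved are plausible in this disease. The protocol describes incomplete recovery from attacks as typical (Section 1.1) and allows for attacks that worsen after diagnosis (Section 4.2.4). What is at stake is the meaning of one exploratory summary. No hypothesis test depends on it.

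**Working it through.** The plan states no figure to reproduce here. The check applies the Table 7-10 rules to every possible score pair.

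**Inputs.** Maximum scores from Table 7-8: ON 7, myelitis 7, brainstem 5, brain 5. Grading rules from Table 7-10, as above. Attack score *a* runs from 1 to the maximum *m*, and follow-up score *f* from 0 to *m*. An attack score of 0 is left out; including it would add only unchanged or worse pairs.

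**Number of pairs.** The total is m(m + 1). Recovered (f < a) is m(m + 1)/2, unchanged is m, and worse is m(m − 1)/2.

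- m = 7: 56 pairs = 28 recovered + 7 unchanged + 21 worse.
- m = 5: 30 pairs = 15 recovered + 5 unchanged + 10 worse.

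**Reading A: improvement = a − f** (a fall in score is positive)

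| Domain | Recovered | Unchanged | Worse |
|---|---|---|---|
| ON | 13 Minor, 15 Major | 7 Minor | 21 Minor |
| Myelitis | 13 Minor, 15 Major | 7 Minor | 21 Minor |
| Brainstem | 9 Minor, 6 Major | 5 Minor | 10 Minor |
| Brain | 5 Minor, 10 Major | 5 ungraded | 10 ungraded |

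Pairs with no recovery that are labelled Minor: 7 + 21 = 28 of 56 in ON and in myelitis, and 5 + 10 = 15 of 30 in brainstem. In Brain, 5 + 10 = 15 of 30 have no grade.

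**Reading B: improvement = f − a** (the usual meaning of change from attack)

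| Domain | Recovered | Unchanged | Worse |
|---|---|---|---|
| ON | 28 Minor | 7 Minor | 11 Minor, 3 Major, 7 ungraded |
| Myelitis | 28 Minor | 7 Minor | 11 Minor, 3 Major, 7 ungraded |
| Brainstem | 15 Minor | 5 Minor | 7 Minor, 3 ungraded |
| Brain | 15 ungraded | 5 ungraded | 4 Minor, 3 Major, 3 ungraded |

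Example: an ON attack scored 6 that returns to 2 gives 6 − 2 = 4 under A (Major) and 2 − 6 = −4 under B (Minor).

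**Common to both readings.** An unchanged score is Minor in ON, myelitis and brainstem, and ungraded in Brain.

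**Which reading fits the table.** Under A, an improvement above 2 cannot occur unless the attack score is at least 3, and an improvement above 1 cannot occur unless it is at least 2. Those are exactly the attack-score conditions in the two Major rows. This points to A as the intended direction, although it is not written.

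**Hand movement.** The protocol records it as its own category, and the Table 11 footnotes treat it as a separate step between counting fingers and light perception. SAP Table 3.5.4-1 also tabulates it by visit. Table 7-8 has no level for it, so such an eye has no ON subscale score for recovery (Table 7-10) or severity (Table 7-9).

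**The case against.** The strongest defence is that this is an exploratory score. Appendix 4 says so, says that no study endpoint rests on attack severity, and leaves the score's usefulness to be judged at the end of the study. Under Reading A the Major group is correct, so a reader who compares Major with everything else is not misled. All of that stands, and it sets the size of the point. It does not answer the main defect: an unchanged score is graded Minor recovery in three domains under either sign.

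Three stronger readings are tempting, and the documents do not support them.

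- *The plan grades a worsening of 3 or more points as Major recovery.* Footnote a writes no subtraction, and the column heading points the other way. Even under Reading B, the Major row also needs an attack score of at least 3. In ON and myelitis only 3 to 6, 3 to 7 and 4 to 7 qualify. In brainstem it is impossible, because the scale stops at 5. Brain has its own cut (2 to 4, 2 to 5 and 3 to 5). Nor can this result be combined with the finding that worsening of every size is Minor, which needs Reading A.
- *The table would show every attack as recovered.* Brain attacks with no gain are ungraded under both readings. The Attack Follow-up Visit (Protocol Section 4.2.5) is required only for attacks that meet the protocol criteria and need rescue treatment, so some adjudicated attacks may have no follow-up score. The documents do not say how many attacks show no gain, so no percentage can be given.
- *Severe visual attacks drop out of the reporting.* They lack a score only in the Appendix 4 tables. SAP Table 3.5.4-1 separately reports hand movement and the other low-vision categories, and acuity change, by visit.

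**Conclusion.** The point holds in limited form. Table 7-10 has no category for no recovery or worsening. In ON, myelitis and brainstem an unchanged score is graded Minor recovery under either sign, and under attack minus follow-up so is every worsening. In Brain these outcomes have no grade. Footnote a leaves the direction open. Read as follow-up minus attack, it conflicts with the heading, makes every true ON, myelitis and brainstem recovery Minor, and leaves every Brain recovery ungraded. It should be treated as an ambiguity, not as a stated wrong sign. The missing hand-movement level is real but secondary.

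The conclusion assumes that the 2-or-less cell is complete as printed. A lower bound of 1, parallel to the Brain row, may have been intended but is not there. The effect is confined to exploratory descriptive summaries. The primary and key secondary analyses, the alpha allocation and the sample size are untouched.

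**What to change.** In SAP Appendix 4:

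1. Replace footnote a with: improvement = subscale score at attack − subscale score at follow-up.
2. Use three grades in Table 7-10: None/worse (0 or below, all domains), Minor (1 to 2; Brain 1) and Major (above 2; Brain above 1).
3. Change the two-grade wording in the Appendix 4 text and in the attack-recovery row of Table 3.5.4-1 to match.
4. State which ON subscale level hand movement takes in Table 7-8.

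With steps 1 and 2, the 28, 28 and 15 unchanged or worse pairs in ON, myelitis and brainstem leave Minor, and the 15 ungraded Brain pairs gain a grade. The cost is a short SAP edit and the matching table specification. It needs no new data.
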